## STUDY FLOW

.	dividuals in the PanelSens database.					
		Inclusion criteria will be men	RECRUITMENT			
	cipate in the experiment, a	(Chemosens platform)				
	gibility will be sent.					
	nformation sheet	
 
Participants will read the infe
 
	INFORMED CONSENT			
	onsent form	
 
Participants will sign the con
 
	(On paper)			
	nly allocated to one of the two	
 
Participants will be randomly
 
				
	L:1)	experimental conditions (1:1	RANDOMISATION			
	Environmental label	No label	(Random Allocation			
	(E)	(X)	Software)			
	dummy virtual supermarket.	
 
Participants will navigate in a du
 
				
n	pants will be asked to go shopping in					
		the supermarket twice to select				
	ns to compose a home-cooked dish					
	·	among 66 products				
	dy-to-eat dish among 30 products	- Task 2: Selection of 1 ready-				
	pe counterbalanced)	(The order of these two tasks will be	SHOPPING TASKS			
to	-	-	(virtual reality			
go shopping in the supermarket twice to select environmentally			headset)			
friendly ready-to-eat dishes:						
- Task 1: Selection of 3 items to compose a home-cooked dish						
among 66 products						
- Task 2: Selection of 1 ready-to-eat dish among 30 products						
(The order of these two tasks will be the same as in the everyday						
scenario)						

 
Under the virtual reality headset, participants will be asked to
 
			FAMILIARITY AND			
evaluate their familiarity and liking of the 8 products they			LIKING OF THE			
	ping tasks.	PRODUCTS SELECTED				
		(virtual reality				
			headset)			
	gather information regarding the	
 
This questionnaire aims to ga
 
				
ty	s underwent under the virtual reality					
	ootential aim-guessers and food					
nts	shopping experience. For participan	motives during the online sh				
	estigate if they paid attention,	Qualtrics				
understood and used the environmental labelling.						
of	e assessed through an adaptation of	FOOD CHOICE				
	naire".	QUESTIONNAIRE				
			Qualtrics			
phic	a questionnaire on socio-demograp	
 
Participants will complete a
 
	SOCIO-			
		DEMOGRAPHIC				
		CHARACTERISTICS				
		Qualtrics				
D D	be counterbalanced) ario (2): Participants will be asked to set twice to select environmentally ins to compose a home-cooked dish dy-to-eat dish among 30 products be the same as in the everyday eadset, participants will be asked to nd liking of the 8 products they oping tasks.	(virtual reality headset) FAMILIARITY AND LIKING OF THE PRODUCTS SELECTED (virtual reality headset) INVESTIGATION QUESTIONNAIRE Qualtrics FOOD CHOICE QUESTIONNAIRE Qualtrics SOCIO- DEMOGRAPHIC CHARACTERISTICS				

The complete study flow is represented in Figure 4.

[figure not shown]

Figure 4. Complete study flow.

## STATISTICAL ANALYSES

All statistical analyses will be performed using SAS version 9.4. The level of significance will be set at p < 0.05 for all pre-registered analyses.

## Definition of the population for analysis

Participants who will be included in the statistical analyses are the ones having completed the shopping tasks and answered all of the questionnaires. Aim-guessers will be excluded in the sensitivity analysis.

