## EXPERIMENTAL DESIGN

[figure not shown]
This study will be a randomised controlled trial with two experimental arms:

[figure not shown]
- 1/ No label (no label condition)
- 2/ Environmental label (label condition)

A 2-block randomisation sequence (male and female) of 1:1 will be generated to allocate each participant to one of the experimental arm before recruitment using the Random Allocation software (Saghaei, 2004).

Each participant will be asked to perform two hypothetical shopping tasks in a virtual shopping environment, first in an "everyday scenario": 1/ choice of 3 ingredients for an everyday home-cooked dish among 66 products, 2/ choice of a ready-to-eat dish for an everyday meal among 30 products. The order of presentation of the two tasks will be counterbalanced. Then, the participants will be asked to perform the same two tasks while choosing foods for a dish that is "good for the planet" ("environmentally-friendly scenario"). For a given participant, the order of presentation of the two tasks will remain the same as in the everyday scenario.

The experimental design is described **Figure 1**.

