### Questionnaires after the shopping experience

After the shopping experience, participants will be asked to complete one questionnaire with the virtual reality headset and four questionnaires on a separate computer (Qualtrics). These questionnaires will be presented in the following order:

- After the four shopping tasks, participants will be asked to evaluate their familiarity and liking of the eight products selected under the virtual reality headset. The eight products will successively appear under the headset and participants will give a familiarity score (frequency of consumption of a similar product, ranging from "never" to "very often") and a liking score (score ranging from 1 to 10) for each product.
- 2) An investigation questionnaire will then be presented to participants on a computer to identify aim-guessers and record participants' feedback about their experience in the virtual supermarket. We will use questions adapted from the *presence questionnaire* used in previous studies (Schnack et al., 2019; Witmer et al., 2005). We will ask participants to evaluate, for each scenario, the importance of the presumed price, taste, packaging size, nutritional quality and environmental impact when making their choices ("not influenced" to "very influenced" by each criteria). For participants in the "label condition", we will also investigate if they paid attention, understood and used the environmental label while selecting products. Participants in the "no label condition" will also be asked if they noticed the presence of an environmental label in the virtual supermarket (*manipulation check*) and if they understand the meaning of the environmental label (displayed in the questionnaire). We will also ask questions to investigate what participants understood when asked to choose an environmentally-friendly dish.

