## Participant's characteristics

Participants' characteristics, overall and for each condition, will be displayed in a table. We will include gender, age, highest educational qualification, current employment, number of people living in the household, the perceived financial status of the household, dieting status and BMI. Continuous variables will be summarised using means and standard deviations. Categorical variables will be summarised using counts and percentages.

Objective	Dependent variables (Y)	Independent variables (x)	Data used	Statistical analysis
1.1. To study the effect of an environmental label on the environmental	Mean of PEF scores for 100g of each ingredient selected and PEF score for 100g of the ready- to-eat dish.	- Environmental label (0= no / 1= yes)	Only data from scenario 1 ("everyday scenario")	Mixed model analysis with random effect of participants. PEF = label (0/1) + type_of_food (I/RTEd) + label*type_of_food

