### Missing data

We do not anticipate missing data for our analysis. It will be impossible for the participant to finish the shopping scenarios without having selected the 8 products. We have calculated the FSA-NPS scores and the PEF score for all of the products presented in our virtual supermarket.

We do not anticipate missing data for the dependent variables because the questionnaires will not allow missing answers. Data from participants who start but do not finish the study will not be included. Any *a posteriori* withdrawal will be reported and reasons for withdrawal will be documented (e.g., incorrect answers, technical problems).

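### The completers-only rule drops participants who stop after the everyday scenario from primary Model 1.1, although that model needs nothing collected later, and no sensitivity analysis tests this

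*Combined protocol and SAP*

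**What the plan says.** Under Definition of the population for analysis, the plan sets this rule: "Participants who will be included in the statistical analyses are the ones having completed the shopping tasks and answered all of the questionnaires". The Missing data section repeats it: "Data from participants who start but do not finish the study will not be included". Neither exempts the primary model.

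For objective 1.1, the table in Overview of the statistical analysis gives the data used as "Only data from scenario 1", which means the everyday scenario. Model 1.1 (Primary analyses) regresses PEF on labelling, type of food and their interaction, with a random participant effect.

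Experimental design puts the everyday tasks first. The environmentally friendly scenario follows: "Then, the participants will be asked to perform the same two tasks while choosing foods for a dish that is". All questionnaires come last, as their own section states: "After the shopping experience, participants will be asked to complete one questionnaire with the virtual reality headset and four questionnaires on a separate computer".

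The Sensitivity analyses section lists three checks on Model 1.1: excluding aim-guessers, adjusting for age, sex, education and BMI, and replacing PEF by GHGe.

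**The concern.** Completion is observed after randomisation and, in the label arm, after the label has been explained and seen. Selecting participants on it can undo the balance that randomisation gives. Here the selection is also avoidable in principle, because the discarded choices are exactly the data Model 1.1 uses. If stopping differs between arms, or if stoppers differ from completers in a way that depends on arm, the estimated label effect is shifted. None of the planned checks would show it.

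**Working it through.** **Step 1: what Model 1.1 needs and what the rule demands, in order of the session.**

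| Stage | Needed for Model 1.1 | Required by the analysis-set rule |
|---|---|---|
| Allocation (Study flow) | yes | yes |
| Everyday tasks: 3 ingredients and 1 ready-to-eat dish | yes | yes |
| Second-scenario tasks | no | yes |
| Familiarity and liking ratings | no | yes |
| Computer questionnaires | no | yes |

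PEF is a property of the product and has already been calculated for all products (Missing data). Once the four everyday choices are recorded, the participant's Model 1.1 data are complete.

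**Step 2: do the sensitivity analyses cover it?** Excluding aim-guessers narrows the set further. Covariate adjustment and the GHGe outcome do not add anyone back. Withdrawals are to be reported with reasons, but no analysis is attached and no breakdown by arm is required.

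**Step 3: is there a figure for stopping in the plan?** No. The nearest figure is in Sample size: 130 − 122 = 8 extra recruits, or 8/130 = 6.2%. They are reserved for data lost through technical problems, which is not a count of people who stop with usable choices.

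**Step 4: illustration of size.** Inputs from the plan: 130 recruited at 1:1, so 65 per arm. Assumed, because the documents give neither: k, the number of later stoppers with recorded everyday PEF, and d, their mean difference from completers in the same arm, in SD units.

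The full-arm mean equals the completer mean plus (k/65) × d. Leaving stoppers out therefore changes the label effect, in absolute size, by

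shift = |k_L × d_L − k_C × d_C| / 65, with L the label arm and C the no-label arm.

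All stoppers in one arm:

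| k | d = 0.5 SD | d = 1 SD |
|---|---|---|
| 2 | 2 × 0.5/65 = 0.015 | 2 × 1/65 = 0.031 |
| 4 | 4 × 0.5/65 = 0.031 | 4 × 1/65 = 0.062 |
| 8 | 8 × 0.5/65 = 0.062 | 8 × 1/65 = 0.123 |

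Stoppers in both arms:
- 4 and 4, same difference: (4 × 0.5 − 4 × 0.5)/65 = 0.
- 4 and 4, opposite differences of 0.5 SD: (4 × 0.5 + 4 × 0.5)/65 = 0.062 SD.

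For scale, the standard error of a two-group difference with one value per participant is √(1/65 + 1/65) = √(2/65) = 0.175 SD. The standard error in Model 1.1 would also depend on the correlation between the two tasks, which the plan does not give. The one-arm range of 0.015 to 0.123 SD is 3% to 25% of the planned effect of d = 0.50 (0.015/0.50 and 0.123/0.50).

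**The case against.** The best reply is that the rule may never bite. Sessions are individual with an experimenter present, people with known nausea or dizziness in a headset are not eligible, and the voucher comes after completion. Questionnaire answers are forced, and the plan notes "It will be impossible for the participant to finish the shopping scenarios without having selected the 8 products". No missing data are anticipated. This stands as an argument about size. Forced answers and compulsory selections prevent gaps in a finished session, but they do not stop someone from leaving. The plan itself writes a rule for people who start and do not finish.

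A second reply is that the choices may not be recoverable. This also stands. Footnote 8 to the exploratory analyses says that time can be identified for each task, which suggests task-level logging. No section says that choices from an interrupted session are kept. Consent terms could not be checked in the text reviewed.

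Three stronger readings are tempting, and the documents do not support them:

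- *The rule costs power.* A reader might compare 80.8% at 130 analysed with 78.2% at 122 (two-sided t-test, d = 0.50). The 8 places between those totals are for technical data loss, and such data might not come back under any rule. The difference is not shown to be a cost of this one.
- *Uneven stopping is likely anyway.* With 8 stoppers and equal stopping chances, a split of 6:2 or worse, in either direction, has probability 28.9%. That is chance imbalance: if stoppers differ from completers equally in both arms, its expected shift is zero. It is not evidence of bias.
- *The rule invites discretionary exclusions,* because incorrect answers are given as an example reason for later withdrawal without a definition. That is a separate gap in detail and adds no weight here.

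**Conclusion.** The point holds as a matter of text: the analysis set demands more than the primary model uses, the exclusion follows randomisation, and no planned analysis tests it. It does not show that the label effect will be biased. Bias requires that some participants stop after the everyday tasks, and that either the stopping or the stoppers' PEF difference from completers differs by arm. The documents establish neither condition. The shifts in the working are assumptions, neither an estimate nor a bound, and even the largest is below one standard error. The rule is worth changing because the change is cheap and protects the randomised comparison, not because serious harm is shown.

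**What to change.** **Change the SAP wording as follows.**

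- For Models 1.1 and 1.2, analyse all randomised eligible participants, in the allocated arm, with recorded PEF for at least one completed task in the scenario or scenarios the model uses, unless consent to use the data is withdrawn. Score task 1 only when all 3 ingredients were chosen, since its PEF is defined as a mean of three. State the missing-at-random assumption.
- Apply the same rule to the Model 2.1 outcomes that come from product data: FSA, NOVA and price per calorie.
- Require questionnaire data only where they are used: liking and familiarity, Model 2.2, adjusted Model 1.1, the aim-guesser analysis and the questionnaire-based exploratory analyses.
- Keep the all-complete set as a sensitivity analysis for Model 1.1, and use it as the comparator for the aim-guesser exclusion. The plan uses the computer questionnaire for that classification ("An investigation questionnaire will then be presented to participants on a computer to identify aim-guessers"), so earlier stoppers cannot be classified.
- Compare adjusted with raw Model 1.1 on the same participants.
- Show the number with missing values in the participant characteristics table, and report exclusions with reasons by arm.

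**Cost.** Denominators will differ between models; BMI trimming can already cause this in adjusted Model 1.1. Restored stoppers will lack socio-demographic questionnaire data, because that questionnaire comes last. The gain depends on the virtual reality system having stored the choices, which the sponsor must confirm, together with consent to use them.

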## Participant's characteristics

Participants' characteristics, overall and for each condition, will be displayed in a table. We will include gender, age, highest educational qualification, current employment, number of people living in the household, the perceived financial status of the household, dieting status and BMI. Continuous variables will be summarised using means and standard deviations. Categorical variables will be summarised using counts and percentages.

Objective	Dependent variables (Y)	Independent variables (x)	Data used	Statistical analysis
1.1. To study the effect of an environmental label on the environmental	Mean of PEF scores for 100g of each ingredient selected and PEF score for 100g of the ready- to-eat dish.	- Environmental label (0= no / 1= yes)	Only data from scenario 1 ("everyday scenario")	Mixed model analysis with random effect of participants. PEF = label (0/1) + type_of_food (I/RTEd) + label*type_of_food

### Overview of the statistical analysis

impact of ingredients and ready-to- eat dish choice in a virtual supermarket.		- Type of food (I  / RTEd  )		If label*type_of_food interaction is not significant, it will be removed from the model.
1.2. To investigate whether the environmental label is informative and likely to help individuals to choose environmental- friendly food options when they are encouraged to make environmental- friendly food choices.	Mean of PEF score for 100g of each ingredient selected and PEF score for 100g of the ready- to-eat dish.	- Environmental label (0= no / 1= yes) - Scenario ("everyday scenario"/ "environmental- friendly scenario") - Type of food (I / RTEd)	Data from the two labelling conditions and the two scenarios	Mixed model analysis with random effect of participants. Mixed model analysis with random effect of participants. PEF = label (0/1) + type_of_food ( I/RTEd ) + scenario (everyday/environmental) + label*type_of_food + label*scenario + scenario*type_of_food Non-significant interactions will be removed from the model. If the labelling*type_of_food or the scenario*type_of_food interaction is statistically significant: • For the 3 ingredients chosen (Task 1) PEF = labelling + scenario + labelling * scenario • For the ready-ot-eat dish chosen (Task 2) PEF = labelling + scenario + labelling * scenario
2.1. To study the effect of an environmental label on the nutritional quality, liking, familiarity, level of process and price of ingredients and ready-to- eat dish choice in a virtual supermarket.	
 
Mean of the FSA scores for 100g of each ingredient selected and FSA score for 100g of the ready-to-eat dish.
 
Average liking of the 3 ingredients selected and liking for the RTEd (continuous variable)
 
Average familiarity of the 3 ingredients selected and familiarity for the RTEd (continuous variable)
 
Average NOVA score of the 3 ingredients
 
	- Environmental label (0= no / 1= yes) - Type of food (I / RTEd)	Data from scenario 1 only (everyday scenario)	Mixed model analysis with random effect of participants. - FSA = label (0/1) + type_of_food (l/RTEd) + (label*type_of_food) - Liking = label (0/1) + type_of_food (l/RTEd) + (label*type_of_food) - Familiarity = label (0/1) + type_of_food (l/RTEd) + (label*type_of_food) - Price per calorie = label (0/1) + type_of_food (l/RTEd) + (label*type_of_food) If the label*type_of_food interaction in model 1.1 is not statistically significant, this

 <sup>4 Ingredient (3 ingredients are chosen by the participant)
  RTEd: ready-to-eat dish

	selected (continuous variable) - Average price per calorie of the 3 ingredients selected and price per calorie for the RTEd (continuous variable)			interaction will not be included in these models. ANOVA model for the 3 ingredients chosen (Task 1): NOVA score = label (0/1)
2.2. To investigate the relationships between food motives and the effect of an environmental label on ingredients and ready-to- eat dish selection in a virtual supermarket.	Mean of PEF scores for 100g of each ingredient selected and PEF score for 100g of the ready- to-eat dish.	
 
Environmental label (0= no / 1= yes)
 
The average ratings for items in the ethical subscale of the FCQ (Ethic_score)
 
Type of food (I / RTEd)
 
	Data from scenario 1 only (everyday scenario)	Mixed model analysis with random effect of participants. - PEF = labelling + Ethic_score + type_of_food + labelling* type_of_food + labelling* Ethic_score If label*type of food interaction is statistically significant: 2 ANCOVA models • For the 3 ingredients chosen (Task 1) - PEF = labelling + Ethic_score + labelling* Ethic_score • For the ready-ot-eat dish chosen (Task 2) - PEF = labelling + Ethic_score + labelling* Ethic_score

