#### Secondary outcomes

 The nutritional quality of the dishes chosen by participants is assessed by the FSA score (the British Food Standards Agency nutrient profiling system) (Rayner et al., 2009), as described for each product (Julia & Hercberg, 2017).

The nutritional quality of the home-cooked dish (j) chosen during task 1 of each scenario is calculated by the mean of the FSA scores of each of the 3 ingredients (i) composing the dish.

$$FSA \ score_j = \frac{\sum_{i=1}^{i=3} FSA_i}{3}$$

 $FSA_i$  scores are calculated for 100g of the ingredient i.

The nutritional quality of the ready-prepared dish chosen (task 2 of each scenario) is assessed by the FSA score for 100g of this product.

• The liking score of the home-cooked dish (j) is the average of the 3 ingredients (i).

$$Liking j = \frac{\sum_{i=1}^{3} liking i}{3}$$

For the ready-to-eat dish, we will directly use the liking score given by participants. The liking score ranges from 1 to 10, 10 being the highest degree of liking.

• The familiarity score of the home-cooked dish is the average of the familiarity score of the 3 ingredients selected.

Familiarity 
$$j = \frac{\sum_{i=1}^{3} familiarity i}{3}$$

The familiarity score of the ready-to-eat dish is directly used. Familiarity scores range from 1 to 5 (1=Never and 5=Very often).

 The NOVA score of the home-cooked dish is the average of the NOVA score of the 3 ingredients selected.

NOVA score 
$$j = \frac{\sum_{i=1}^{3} NOVA \ score \ i}{3}$$

The NOVA score of the ready-to-eat dish will not be analysed since, by definition, all of these foods will be categorised in category 4 (ultra-processed foods).

• The price per calorie of the home-cooked dish is the average of the price per calorie of the 3 ingredients selected. The price per calorie of the ready-to-eat dish is directly used.

Price 
$$\left(\frac{\epsilon}{kcal}\right) j = \frac{\sum_{i=1}^{3} price \ per \ calorie \ i}{3}$$

The price per calorie for one product will be calculated with the following equation:

$$Price \ per \ calorie_i \ (\frac{\epsilon}{kcal}) = \frac{Price_i(\epsilon) \times 100}{Weight_i(g) \times Energy \ density_i(\frac{kcal}{100g})}$$

Independent variables

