### Primary analyses

**MODEL 1.1:** Mixed model analysis will be used to test the effect of *labelling* (categorical variable: yes or no), *type\_of\_food* (categorical variable: ingredients or ready-to-eat dish) and *labelling\* type\_of\_food interaction* on PEF scores in the "everyday scenario", with random effect of participants to account for correlation between repeated measures. If the *labelling\*type\_of\_food interaction* is not significant, it will be removed from the model.

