### Secondary analyses

For the first secondary analysis (MODEL 2.1), mixed model analysis will be used to test the effect of *labelling* (categorical variable: yes or no), *type\_of\_food* (categorical variable: ingredients or ready-to-eat dish) and *labelling\*type\_of\_food* interaction on 4 dependent variables, with random effect of participants to account for correlation between repeated measures. We will only look at the data from the first scenario ("everyday scenario"). The 5 mixed model analysis that will be carried out are:

- FSA = labelling (categorical variable: yes or no), type\_of\_food (categorical variable: ingredients or ready-to-eat dish) and labelling\* type\_of\_food interaction
- Liking = labelling (categorical variable: yes or no), type\_of\_food (categorical variable: ingredients or ready-to-eat dish) and labelling \* type\_of\_food interaction
- Familiarity = labelling (categorical variable: yes or no), type\_of\_food (categorical variable: ingredients or ready-to-eat dish) and labelling\* type\_of\_food interaction
- Price per calories (€/kcal) = labelling (categorical variable: yes or no), type\_of\_food (categorical variable: ingredients or ready-to-eat dish) and labelling\* type\_of\_food interaction

If the *labelling\*type\_of\_food interaction* is not significant, it will be removed from the models.

ANOVA model will be used to test the effect of *labelling* (categorical variable: yes or no) on NOVA score for task 1 (for the 3 ingredients chosen). We will only look at the data from the first scenario ("everyday scenario").

- For the second secondary analysis (**MODEL 2.2**), we will only use "everyday scenario" data.
  - Mixed model analysis will be used to test the effect of *labelling* (categorical variable: yes or no), *type\_of\_food* (categorical variable: ingredients or ready-to-eat dish), *labelling\*type\_of\_food* interaction, *Ethic\_score* (continuous variable) and *labelling\* Ethic\_score* interaction on PEF scores, with random effect of participants to account for correlation between repeated measures. If the *labelling\*type\_of\_food* interaction is not significant, it will be removed from the model.

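### Model 2.1 has two conflicting rules for keeping the label-by-food-type interaction, and the overview table's rule makes that choice depend on the PEF result

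*Combined protocol and SAP*

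**What the plan says.** **Overview of the statistical analysis, objective 2.1.** The table lists mixed models for FSA, liking, familiarity and price per calorie, each with `label*type_of_food` in brackets. It then sets a condition, "If the label*type_of_food interaction in model 1.1 is not statistically significant", in which case this "interaction will not be included in these models". The condition concerns PEF. The consequence falls on four other outcomes.

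**Secondary analyses, Model 2.1.** The text says that mixed models will test labelling, food type and their "interaction on 4 dependent variables, with random effect of participants to account for correlation between repeated measures". It lists the same four models, each with the interaction. If the interaction "is not significant, it will be removed from the models". Model 1.1 is not mentioned.

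**Primary analyses, Model 1.1.** The PEF interaction is fitted on everyday-scenario data and, if it "is not significant, it will be removed from the model".

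**NOVA** is outside the conflict. "The NOVA score of the ready-to-eat dish will not be analysed", so it has a label-only ANOVA on the ingredients.

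No section says whether the table or the text takes precedence.

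**The concern.** The two places differ in what triggers exclusion (the PEF interaction, or an interaction fitted on the secondary outcomes) and in what is then done (never entered, or entered and removed). Two analysts who follow the plan in good faith can therefore report different models, and the choice could be made after seeing the data.

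The table's rule is also a poor one in its own right. PEF measures environmental impact. A similar label effect on PEF in both tasks does not imply similar effects on nutritional quality, liking, familiarity or price. The tasks differ in structure (three of 66 ingredients against one of 30 dishes), and objective 2.1 asks about both kinds of choice. Under the table's rule, a difference between tasks in these outcomes can go unexamined for a reason unrelated to them.

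**Working it through.** The plan gives no figure for this point, so the check has two parts: the two rules side by side, then an illustration of size.

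**1. Final model under each rule**

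| PEF interaction (Model 1.1) | Interaction on the secondary outcome | Overview table | Secondary analyses text | Same final model? |
|---|---|---|---|---|
| not significant | not significant | not entered | fitted, then removed | yes |
| significant | significant | entered | kept | yes |
| not significant | significant | not entered | kept | no |
| significant | not significant | entered, no rule to drop it | removed | no |

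The rules agree only when both interactions are significant or both are not.

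**2. Inputs for the illustration**

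- From the Sample size section: 122 participants required and d = 0.50 for labelling on PEF. With 1:1 allocation (Experimental design), that is 122/2 = 61 per arm.
- From Statistical analyses: "The level of significance will be set at p < 0.05 for all pre-registered analyses". Sidedness is not stated; two-sided is assumed.
- Assumed, because the documents give no value: equal SDs in the two tasks, between-task correlation ρ of 0 to 0.3, an interaction of 0.5 SD (difference between the two tasks' label effects), and independence between PEF and the secondary outcome.

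As a background check on the method, a two-sample noncentral t calculation with 61 per arm and d = 0.50 gives 78.2% power, close to the plan's 80%. The point does not rest on this.

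**3. Power of the interaction test**

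Each participant does both tasks, so the test is a two-sample t-test on the within-person difference between tasks. That difference has SD √(2(1−ρ)) in units of the outcome SD. The standardised effect is 0.5/√(2(1−ρ)), and the noncentrality is that value times √(61/2) = 5.523, on 120 degrees of freedom.

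- ρ = 0: 0.5/1.414 = 0.354; noncentrality 1.95; power 49.1%.
- ρ = 0.3: 0.5/1.183 = 0.423; noncentrality 2.33; power 63.9%.

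**4. How often the table's rule omits the term**

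- No true PEF interaction: 1 − 0.05 = 95%.
- True PEF interaction of 0.5 SD: 1 − 0.491 = 51% (ρ = 0) and 1 − 0.639 = 36% (ρ = 0.3).

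**5. Chance of detecting a 0.5 SD interaction on one secondary outcome**

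- Tested in its own model (the text's rule): 49% to 64%.
- Table's rule, no true PEF interaction: 0.05 × 0.491 = 2.5% to 0.05 × 0.639 = 3.2%.
- Table's rule, PEF interaction also 0.5 SD: 0.491² = 24% to 0.639² = 41%.

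**6. What the table's rule gains**

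With no true interaction anywhere and four independent outcomes, the chance of at least one false-positive interaction is 1 − 0.95⁴ = 18.5% under the text's rule, against 0.05 × 18.5% = 0.9% under the table's.

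**The case against.** **The two sentences might be reconciled.** The text does not say in so many words that significance is judged separately in each model, and the table's brackets mark the term as conditional. One could enter the term only if Model 1.1 is significant and then drop it if it is not significant in its own model. This does not work as a reading of the plan: the text tests the interaction on the four outcomes without any precondition, and a term has to be fitted before it can be removed. It does show that a single sentence could settle the matter.

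**The plan expects a PEF interaction.** Objective 1.1 hypothesises a larger label effect for the ready-to-eat dish. This stands. A reader might infer from the 95% figure that the table's rule would almost always suppress the term, but that figure holds only if the hypothesis is false. With a 0.5 SD PEF interaction the range is 36% to 51%.

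**Limiting interaction tests has value.** This also stands: 0.9% against 18.5% is a real reduction in false positives, and objective 2.1 states no task-specific hypothesis. But the plan does not give this as its reason, and the PEF result is not a relevant criterion for the other outcomes. Estimating the effects, instead of selecting a model on an interaction p-value, avoids the problem differently.

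**Consistency across models.** Keeping the term regardless of its p-value in Model 2.1 departs from the removal rule used for Models 1.1, 1.2 and 2.2. That is a fair cost, and the reason this form of the fix is a preference and not a necessity.

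**Conclusion.** The contradiction is real and needs reconciling, and the table's dependence on PEF is the weaker of the two rules. Under the stated assumptions, a 0.5 SD interaction on a secondary outcome is detected with 49% to 64% power in its own model. Under the table's rule the figure is 2.5% to 3.2% if PEF has no interaction, and 24% to 41% if PEF has an equal one. These figures depend on equal SDs in the two tasks, which is uncertain because the ingredient outcome averages three items and the dish outcome is a single item. They also depend on ρ between 0 and 0.3 and on independence between outcomes.

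The documents do not support three stronger readings:

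- A reader might infer that opposite label effects in the two tasks would cancel, so that objective 2.1 would wrongly report no side effect. Exact cancellation is a special case that also needs equal SDs, and nothing in the plan suggests opposite effects.
- A reader might charge the table's rule with the full gap between an averaged test and an unconditional test in each task. Neither rule prescribes the latter for Model 2.1, and the text's rule also drops a non-significant interaction.
- A reader might infer that the main results are at risk. The conflict is confined to four secondary outcomes. The primary models and NOVA are unaffected, and the equally weighted averaged label estimate is the same with or without the term, because every analysed participant has both tasks.

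**What to change.** Delete the sentence in the overview table that ties Model 2.1 to the Model 1.1 result, and state one rule in identical terms in the table and in Secondary analyses.

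Preferably, keep `label*type_of_food` in all four Model 2.1 mixed models whatever its p-value. Report the label effect averaged with equal weight over the two tasks, and separately for each task, with 95% CIs, and label the per-task estimates descriptive. The minimum acceptable change is to say in both places that the interaction is judged within each outcome's own model. That removes the contradiction but keeps model selection by p-value and the 18.5% false-positive figure above.

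The cost is a change of wording and a few extra table rows. The drawback of the preferred version is more secondary estimates without multiplicity control, which the descriptive label acknowledges. The averaged estimate does not change.
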